9.2.5. Lost to Follow-up

Enrolled pregnancies for which outcome information is unobtainable will be considered lost to follow-up. Before a case is considered lost to follow-up, the registry must make a minimum of monthly contact attempts over 6 months following the EDD to obtain pregnancy outcome information from the HCP. The registry will communicate with the HCP using the HCP's preferred contact method. If there is no response from the HCP, the registry will use other available contact methods based on past experience. Modes of communication with the HCP may include mail, fax, telephone, and email. The available modes of communication with the HCPs are intended to be uniform across countries in which the study will be conducted. Any changes to this imposed by a local IRB or ethics committee will be noted in interim and final study reports.

If the registry is unable to obtain the outcome of the pregnancy from the HCP, the registry may contact the participant or the secondary contact for outcome information, if consistent with local regulations.

9.2.6. Study Awareness and Outreach

Study awareness and retention initiatives will be conducted by the registries, as local regulations allow, and implemented under Biogen Epidemiology and Global Medical Safety guidance.

CONFIDENTIAL

Steps to ensure recruitment and retention of participants will be implemented at the start of the study and may be modified as the study progresses and new enrollment information becomes available.

Active outreach will occur to increase awareness of the study and obtain reports of participants in the registries who were exposed to nusinersen during pregnancy or during the exposure window. Outreach efforts may include the following, as local regulations allow:

- Notification about the study to HCPs and patients currently participating in the registries. The following methods of communication may be used:
 - ISMAR-US, UK Adult SMA-REACH, and SMArtCARE registry websites
 - Newsletters to participants in the ISMAR-US, UK Adult SMA-REACH and SMArtCARE registries
 - FDA website listing pregnancy registries
 - National Institutes of Health ClinicalTrials.gov website
 - Patient advocacy groups
 - Scientific conferences
- Study and site engagement plan to help HCPs see the value of the study data

Apart from these potential methods of outreach, other methods will be explored, as needed. Potential recruitment efforts may also include digital and social media outreach, subject to internal compliance review and local regulations. All outreach methods will be approved by the appropriate review bodies. Awareness activities and content will be evaluated on a regular basis to ensure that target populations are being reached while minimizing burden on the recipients.

Retention will be optimized by monitoring the projected versus observed drop-out rates for the study and by modifying retention efforts for HCPs and participants as needed. In addition, a flexible follow-up schedule (e.g., telephone interviews) will be employed to allow for more convenient data collection and reduce the burden on participants and HCPs.

9.2.7. Withdrawal of Consent

Each participant or their legally authorized representative (where allowed per local regulations) has the right to withdraw consent from the study. Participation in the study will terminate immediately upon the participant's request. The registry will facilitate the withdrawal of consent process. The participant's medical data collected up until the time that consent is withdrawn will be retained and used in the study. If a participant is withdrawn from the study, Biogen's routine spontaneous postmarketing surveillance follow-up procedures will be followed (as required by local drug safety regulations) outside of this for any pregnancy outcomes and AEs.

9.2.8. Sponsor Termination of the Study

Biogen will continue the study until one or more of the following occurs:

- The feasibility of collecting sufficient information has diminished to unacceptable levels because of low exposure rates, poor enrollment, or loss to follow-up (see Section 9.2.5).
- Other methods of gathering appropriate information (e.g., electronic medical record databases) become achievable or are deemed preferable.

Early termination of the study would occur with the agreement of the appropriate regulatory authorities.

9.3. Variables

Each of the following variables will be collected and reported separately.

9.3.1. Variable Definitions

9.3.1.1. Pregnancy Loss

9.3.1.1.1. Pregnancy Termination

A pregnancy termination is defined as any induced or voluntary fetal loss during pregnancy. If possible, the reason for pregnancy termination (e.g., related to SMA, nusinersen, other) should be collected. If available, data from gross or pathologic examination of the abortus or fetus will be evaluated for structural or chromosomal defects.

9.3.1.1.2. Spontaneous Abortion

Spontaneous abortion is defined as any loss of a fetus due to natural causes at < 20 weeks of gestation [FDA 2002, 2019]. If available, data from gross or pathologic examination of the abortus or fetus will be evaluated for structural or chromosomal defects.

9.3.1.1.3. Fetal Death or Stillbirth

Fetal death or stillbirth refers to the death of a fetus prior to complete expulsion or extraction from the mother at ≥ 20 weeks of gestation [FDA 2019] (or at ≥ 350 g if gestational age is unknown). The death is indicated by the fact that, after separation from the mother, the fetus does not show any evidence of life (e.g., heartbeat, umbilical cord pulsation, or definite movement of voluntary muscles). Fetal death occurring at ≥ 20 weeks but < 28 weeks of gestation is considered an early fetal loss. Fetal death occurring at ≥ 28 weeks is considered a late fetal loss.

In the event of a stillbirth or maternal death, full pathology details will be requested, if conducted. If available, data from gross or pathologic examination of the abortus or fetus will be evaluated for structural or chromosomal defects. The final classification between fetal death or stillbirth and spontaneous abortion will be made based on gestational age. If

these parameters are not available, the study will accept the classification indicated by the HCP.

9.3.1.2. Live Birth

A live birth refers to a complete expulsion or extraction from its mother of a surviving neonate breathing or showing any other evidence of life, such as heartbeat, umbilical cord pulsation, or definite movement of voluntary muscles, whether the umbilical cord has been cut or the placenta is attached. Death occurring after birth will be classified as described in Section 9.3.1.9, Section 9.3.1.10, and Section 9.3.1.11. Premature birth and full-term birth will be reported. Preterm birth will also be reported, defined as delivery at < 37 weeks gestation.

9.3.1.3. Birth Weight (Including Small for Gestational Age)

All live births will be classified as small, appropriate, or large for gestational age using the CDC definition of birth weight below the 10th percentile, between the 10th and 90th percentile, and above the 90th percentile, respectively. An infant's birth weight percentile and size for gestational age categorization will be based on World Health Organization growth charts or country-specific growth charts, as appropriate. Low birth weight (< 2500 g) will also be examined as an adverse pregnancy outcome.

9.3.1.4. Major Congenital Malformations

MCMs (interchangeably referred to as congenital malformations, congenital anomalies, and birth defects) are abnormalities in structural development that are medically or cosmetically significant, are present at birth, and persist in postnatal life unless or until repaired, as evaluated by independent advisors (see Section 9.7.5).

All potential MCMs, including minor anomalies, from all countries in which the study will be conducted will be evaluated by a qualified independent teratologist or other appropriate MCM evaluator using all available medical records. The classification of all potential MCMs used in analyses will be based upon the teratologist's adjudication. The exact grouping of MCMs (e.g., major versus minor defects) will vary by analysis in order to mirror the classification systems used in the selected external comparator groups. Minor malformations, chromosomal abnormalities, genetic syndromes, positional defects, and prematurity-related defects will be excluded from major malformations in the primary analyses.

The major birth defect classification system used in this study will align with the choice of external comparator. For example, comparisons of the nusinersen-exposed participants to EUROCAT estimates will be consistent with the EUROCAT classification schema and the EMA pregnancy guidance. Similarly, the MACDP classification will be used when comparing to the MACDP external comparator. All cases will be reviewed based on earliest exposure to nusinersen.

9.3.1.5. Minor Congenital Malformation

Minor congenital malformation is defined as a structural abnormality present at birth that has a minimal effect on clinical function but may have a cosmetic effect.

9.3.1.6. Ectopic Pregnancies

Any reported ectopic pregnancy (defined as a pregnancy that occurs outside of the uterine cavity) will be subclassified in the respective pregnancy outcome, including induced termination, maternal death, or spontaneous pregnancy loss.

9.3.1.7. Molar Pregnancies

Any reported molar pregnancy (defined as genetically abnormal conceptions characterized by abnormal chorionic villi, trophoblastic hyperplasia, poor fetal development, and an increased risk of malignant disease development) will be subclassified in the respective pregnancy outcome, including induced termination, maternal death, or spontaneous pregnancy loss.

9.3.1.8. Maternal Death

The study defines maternal death as death of a pregnant individual during pregnancy, labor, or delivery. The study will also report maternal deaths that occur up to 12 weeks after delivery. In the event of maternal death, full pathology details will be requested.

9.3.1.9. Neonatal Death

The study defines a neonatal death as death occurring in a newborn prior to 28 days after birth. In the event of neonatal death, full pathology details will be requested. Any structural or congenital defect detected in the gross or pathologic examination of the deceased newborn will be evaluated.

9.3.1.10. Perinatal Death

The study defines perinatal death as death occurring at or after 28 days and prior to 12 weeks after birth. In the event of perinatal death, full pathology details will be requested. Any structural or congenital defect detected in the gross or pathologic examination of the deceased newborn will be evaluated.

9.3.1.11. Infant Death

The study defines infant death as death occurring between 12 and 52 weeks after birth, inclusive. In the event of infant death, full pathology details will be requested. Any structural or congenital defect detected in the gross or pathologic examination of the deceased infant will be evaluated.

9.3.1.12. Abnormal Postnatal Growth and Development

Domains of developmental milestones (i.e., social/emotional, language/communication, neurocognitive, movement/physical development milestones) by age up to 52 weeks will be defined by guidelines provided by the CDC [CDC 2020]. As recommended by the

CONFIDENTIAL

CDC, the World Health Organization Growth Charts (suitable for use in the US from birth to 24 months) will be applied for this study, where infant growth measurements will be used to estimate gender-specific weight-for-length, head circumference-for-age, length-for-age, and weight-for-age percentiles.

Postnatal growth deficiency or FTT will be defined as weight in the < 10th percentile for sex and chronological age using international growth reference standards from WHO for children aged 0 to 24 months. Postnatal growth deficiency will be evaluated at 1, 2, 6, 12, 18, and 24 months of age.

Infant developmental deficiency will be defined as failure to achieve developmental milestones for chronological age defined by CDC. Infant developmental deficiency will be evaluated at 1, 2, 6, 12, 18, and 24 months of age.

Developmental milestones will be collected as part of routine clinical practice with pediatrician-determined results of infant status (i.e., below, above, or at age-appropriate achievement) in each of the domains listed above. "Ages and Stages" or similar standardized assessments may be collected for this study if performed as part of routine clinical care. No additional information will be mandated for collection as part of this study.

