9.4. Data Sources

Data will be participant- and clinician-reported. The registries will collect data from participants with SMA who are enrolled in the ISMAR-US, UK Adult SMA-REACH, and SMArtCARE SMA registries if they become pregnant within the relevant exposure window for nusinersen. Participants will be consented and enrolled through the registries (see information on informed consent in Section 10.2). The registries will also collect data from the participants' HCPs (e.g., obstetrician, pediatrician) and electronic medical records. In addition, previously collected data for the participant from the registry will be used. Biogen will receive data in the form of aggregate summary tables.

It is expected that participants and HCPs will be contacted according to the details outlined in Section 9.3.2 and the recommended study contact schedule (Section 16). While contacts for this study are not mandated, registries will inform participants and HCPs of the expected contact schedule and make every effort to ensure data are entered for each expected contact.

If the sample size allows for comparative analysis, reporting rates from the study will be compared with available background rates for pregnancy outcomes in women without SMA who were not exposed to nusinersen using the MACDP and EUROCAT general population databases, as appropriate (see Section 9.7.3.2).

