9.5. Study Size

The goal of the research initiative is to enroll as many participants with SMA who receive nusinersen during pregnancy (or within the relevant exposure window) as possible. Based on the number of individuals of childbearing potential currently enrolled in the registries or who come of childbearing age over the duration of the study and the number of incident pregnancies observed in the registries to date, the estimated enrollment number over the 10-year study period is 20 pregnancies.

As of August 2024, the UK Adult SMA-REACH registry has approximately 285 genetically confirmed SMA patients with 72 using nusinersen [Walker 2024]. In the SMArtCARE registry, as of May 2021, there were 965 SMA patients enrolled. This includes 147 women of childbearing age, of whom 117 have been treated with nusinersen.

While enrollment may slow over time, some increase in new patients is expected in all of the registries. In addition to newly enrolled patients, younger patients are expected to reach childbearing age over the next few years. Together, these factors should lead to an increase in individuals of childbearing age in the registries, which will increase the likelihood of capturing incident pregnancies.

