9.7. Data Analysis

9.7.1. General Discussion of the Analysis

All participants will be reviewed based on earliest exposure within the relevant nusinersen exposure window.

The registries and Biogen Epidemiology and Global Safety will carefully review each pregnancy outcome and the frequency of adverse pregnancy outcomes. For this study, gestational weeks are calculated beginning from the first day of the participant's LMP. If the date of LMP is not available, the EDD may be used. If the gestational week is

inconsistent with the exposure dates and/or the dates of outcomes (outside of 1 week for the first trimester, outside of 2 weeks for the second and third trimesters) and a corrected EDD (i.e., generally by ultrasound) is available, the corrected EDD is used for gestational week calculations.

Descriptive analyses will be performed to analyze the risks of MCMs, spontaneous abortions, SGA births, and abnormal postnatal growth and development.

Statistical analyses may be performed to examine potential increases in risks of MCMs, spontaneous abortions, SGA births, and abnormal postnatal growth and development as compared with the expected background prevalence. The prevalence and 95% CIs for study participants may be calculated to assess the presence of any excessive risk associated with nusinersen exposure.

All analyses will be conducted on an overall basis as well as grouped by the earliest trimester of exposure. For MCMs, analyses will be conducted only for participants who have exposure in the first trimester. In the absence of treatment initiation during the second and third trimester of pregnancy, the subgroups with small sample sizes may be collapsed as needed. Other adverse pregnancy outcomes will be examined similarly as the sample size permits.

A periodic review of the study will be performed by monitoring reports of adverse pregnancy outcomes for nusinersen (see Section 9.7.4).

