9.7.3.1.4. Abnormal Postnatal Growth and Development

The prevalence of abnormal postnatal growth and development reported to the study will be calculated by dividing the number of events of abnormal postnatal growth and development by the total number of live births. If sufficient enrollment numbers are obtained, analysis of abnormal postnatal growth and development may be stratified by earliest trimester of exposure, gestational age at enrollment, maternal age, medical condition, and other maternal risk factors, as appropriate. Sensitivity analyses may be performed for abnormal postnatal growth and development and may be stratified by each trimester, along with the above factors, when the sample size allows.

The 95% CIs for abnormal postnatal growth and development rates will be calculated based on the binomial distribution. If sufficient enrollment numbers are obtained, abnormal postnatal growth and development rates may also be presented in subgroups by

the earliest trimester of exposure, gestational age at enrollment, maternal age, medical condition, and other maternal risk factors at enrollment, as appropriate.

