9.7.3.2. Comparative Analysis

As appropriate and where the sample size permits, MCM reporting rates, spontaneous abortion, SGA births, and abnormal postnatal growth and development rates from the study may be compared with their respective rates in the MACDP and EUROCAT general population databases, acknowledging the limitations of the databases. Robust SMA population-based reporting rates drawn from large SMA populations are unavailable, and rates from the general population remain the primary estimates with which comparisons can be made.

In order to minimize the differences between the comparison groups, subgroup analyses may be conducted, as appropriate, on subsets of the study defined by factors that better reflect the underlying population of the external data sources, such as age and nationality (e.g., within the EU, birth defect rates in the study compared to the general population via EUROCAT).

Comparative analyses will include only prospective reports (i.e., reports received before the outcome of the pregnancy is known). These comparisons will be based on examination of point estimates and 95% CIs. In addition to comparisons of infant outcomes (i.e., MCMs) based on events ascertained up to 52 weeks after birth, comparisons will be based on infant outcomes ascertained up to 12 weeks after birth in order to mirror the ascertainment period used in previous Biogen pregnancy registries.

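### The growth-deficiency prevalence turns six weight checks into one rate without fixing the unit or the age, so it has no usable background value

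*Protocol*

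**What the plan says.** Protocol section 9.3.1.12 gives the case definition: "Postnatal growth deficiency or FTT will be defined as weight in the < 10th percentile for sex and chronological age", using WHO standards for 0 to 24 months. It adds: "Postnatal growth deficiency will be evaluated at 1, 2, 6, 12, 18, and 24 months of age". It asks for no second low reading, persistence or fall across percentiles. Developmental deficiency is defined in the same section and evaluated at the same six ages.

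Section 9.7.3.1.4 obtains the prevalence by "dividing the number of events of abnormal postnatal growth and development by the total number of live births". On the interval it says: "The 95% CIs for abnormal postnatal growth and development rates will be calculated based on the binomial distribution". It names no infant age, no rule for combining the six evaluations and no rule for repeated events in one infant. Growth and development share the one rate.

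Section 9.7.3 commits to this prevalence and interval. Section 9.7.1 allows statistical analyses for increased risk "as compared with the expected background prevalence", and section 9.7.3.2 says that "abnormal postnatal growth and development rates from the study may be compared with their respective rates in the MACDP and EUROCAT general population databases". Both are optional.

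**The concern.** A 10th-percentile cut-off has a known background only at one age and for one weight per infant: 10% of a population that matches the reference. Once six evaluations feed one rate, the background depends on how they are combined, and section 9.7.3.1.4 leaves that open. Its wording can mean a rate at one age, the share of infants ever low, or a count of low weights. In the same healthy infants these give quite different figures.

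The interval has the same problem. A binomial CI needs one yes/no result per infant, whereas the stated numerator is events, and one infant can supply up to six for weight alone.

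The denominator adds a second difficulty. Weights come from routine contacts, and section 9.4 says: "While contacts for this study are not mandated, registries will inform participants and HCPs of the expected contact schedule". An infant who is never weighed stays in the live-birth denominator and so counts as normal.

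At stake is whether one of the four outcomes with a committed prevalence can be interpreted, particularly if it is later set beside a background rate.

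**Working it through.** The protocol states no expected prevalence for growth deficiency, so there is no figure of its own to reproduce.

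**Inputs from the protocol**
- Cut-off: 10th percentile, so probability 0.10 per age in reference infants; c = -1.2816 on the z scale (9.3.1.12).
- Six ages: 1, 2, 6, 12, 18 and 24 months (9.3.1.12).
- Rate: events / total live births, binomial CI (9.7.3.1.4).
- Size: "the estimated enrollment number over the 10-year study period is 20 pregnancies" (9.5), taken here as at most 20 live births, barring multiples.

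**Assumptions, not in the protocol**: infants match the WHO reference, weight z-scores are jointly normal, and the between-age correlation r is as shown.

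**Reading 1, one age.** P = 0.10. Expected low infants: 20 × 0.10 = 2.

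**Reading 2, ever low at six ages.** With no correlation, 1 - 0.9^6 = 0.469, an upper bound. With equal correlation r, P = 1 - ∫ φ(u) [1 - Φ((c - √r·u)/√(1 - r))]^6 du:

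| r | all six weights | three weights only |
|---|---|---|
| 0.95 | 15.6% | 13.5% |
| 0.90 | 18.2% | 15.0% |
| 0.80 | 22.3% | 17.2% |
| 0.70 | 25.8% | 19.0% |
| 0.60 | 29.0% | 20.5% |

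If correlation decays from visit to visit (simulation, 2,000,000 infants), neighbouring-visit values of 0.95 to 0.75 give 18.0% to 29.4%; 0.70 gives 31.4%. If it decays with log age, with 0.78 to 0.36 between 1 and 24 months, the result is 18.0% to 26.2%. So about 16% to 30% is a fair working range. In 20 live births that is 20 × 0.156 = 3.1 to 20 × 0.30 = 6.0 infants, against 2 at one age.

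**Reading 3, every low weight is an event.** Expected events per infant are 6 × 0.10 = 0.60, whatever the correlation. For 20 infants that is 20 × 0.60 = 12 events, from a possible 6 × 20 = 120. Each infant contributes 0 to 6 correlated events, so the number of live births is not the number of binomial trials.

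**Denominator.** If a fraction f of live births is weighed at an age, the expected rate over all live births is 0.10 × f. For illustration, with 15 of 20 weighed, 1.5/20 = 7.5%, whereas 1.5/15 = 10%.

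**Precision.** Exact 95% CIs with 20 infants: 2/20, 1.2% to 31.7%; 4/20, 5.7% to 43.7%; 5/20, 8.7% to 49.1%; 6/20, 11.9% to 54.3%. Only the last excludes 10%.

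**Persistence rules.** In the same models, two consecutive low weights occur in about 9% to 15% of healthy infants, and any two of six in about 12% to 16%. These rates also depend on the assumed correlation.

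**The case against.** The strongest reply is that the protocol nowhere makes an infant a case on one low weight at any of six ages. Section 9.3.1.12 says when growth is evaluated, and reporting at each age, which keeps the healthy rate at 10%, is not ruled out. A reader might infer a best-of-six rule and conclude that a two- to three-fold false excess is built in. The documents do not support that. The rule is an inference, and the size depends on an unstated correlation, on complete weights and on infants who match the reference. No 10% comparator is written down, and the external comparison is optional. Section 9.9 already lists duration of follow-up among the differences that can bias such comparisons. With about 20 infants, most plausible counts could not be told apart from 10%. The pooled rate also includes developmental deficiency, so the growth calculation is not the reported quantity. All of this stands.

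It can also be said that combining repeated evaluations is work for the statistical analysis plan, to which section 9.7.3 leaves analysis details. That answers only part of the point. The case definition, the numerator, the denominator and the interval method are written in the protocol, and a later plan would have to override events over live births rather than fill a gap.

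Finally, requiring two consecutive low weights would not be a clean cure: its healthy rate is not fixed at 10%, and with contacts not mandated some low weights would never be confirmed.

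**Conclusion.** The point holds in a limited form. The protocol fixes a formula whose value in healthy infants could be 10%, about 16% to 30%, or 0.6 events per infant, depending on a choice that it does not state. Under the event count, which is the literal wording, the binomial interval is not valid. Under any reading, using all live births as the denominator pulls the rate down when weights are missing.

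The 10% and the 0.6 need only infants who match the WHO reference, and the 0.6 also needs all six weights. The 16% to 30% needs both of these and an assumed between-age correlation of about 0.95 down to 0.6-0.7; with three weights it is about 13% to 20%. The consequence is a rate without a usable background, not a demonstrated false signal. Correcting it is a cheap improvement.

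**What to change.** In sections 9.3.1.12 and 9.7.3.1.4:

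- Report growth deficiency separately from developmental deficiency.
- At each scheduled age, give the proportion of infants below the 10th percentile among infants weighed at that age, with the number weighed and a binomial CI, read against the 10% that the reference fixes. The limits in section 9.9 on separating SMA from nusinersen still apply to that reading.
- If one infant-level figure is also wanted, count each infant once, label it as ever low or persistent, do not compare it with a single-age background rate, and show it with and without infants who were SGA at birth, since SGA is already a separate outcome in section 9.7.3.1.3.

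The cost is wording only, because section 9.3.2.5 already collects weight at all six ages. The downside is several small by-age estimates with wide intervals (2 of 20 gives 1.2% to 31.7%) instead of one.

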9.7.3.1.3. Small for Gestational Age Births

The prevalence of SGA births reported to the study will be calculated by dividing the number of SGA births by the total number of live births. If sufficient enrollment numbers are obtained, analysis of SGA births may be stratified by earliest trimester of exposure, gestational age at enrollment, maternal age, medical condition, and other maternal risk factors, as appropriate. Sensitivity analyses may be performed for SGA births and may be stratified by each trimester, along with these factors, when the sample size allows.

The 95% CIs for SGA birth rates will be calculated based on the binomial distribution. If sufficient enrollment numbers are obtained, SGA birth rates may also be presented in subgroups by the earliest trimester of exposure, gestational age at enrollment, maternal age, medical condition, and other maternal risk factors at enrollment, as appropriate.

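### Postnatal growth deficiency is defined by attained weight alone, so this component overlaps with SGA and does not by itself separate smallness at birth from impaired growth after birth

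*Protocol*

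**What the plan says.** Section 9.3.1.12 gives the definition: "Postnatal growth deficiency or FTT will be defined as weight in the < 10th percentile for sex and chronological age". The reference is the WHO standard covering the first two years of life. The rule is applied repeatedly: "Postnatal growth deficiency will be evaluated at 1, 2, 6, 12, 18, and 24 months of age". The section also has "weight-for-length, head circumference-for-age, length-for-age, and weight-for-age percentiles" estimated, but only weight enters the definition.

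Section 9.3.1.3 classifies a live birth as SGA "using the CDC definition of birth weight below the 10th percentile". The birth percentile "will be based on World Health Organization growth charts or country-specific growth charts, as appropriate".

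Both outcomes share a denominator. SGA prevalence is found by "dividing the number of SGA births by the total number of live births" (section 9.7.3.1.3). The postnatal rate is found by "dividing the number of events of abnormal postnatal growth and development by the total number of live births" (section 9.7.3.1.4). Section 9.7.3.1.4 lists several stratification factors; SGA status at birth is not one of them, and SGA infants are not excluded. The postnatal outcome also covers developmental deficiency, so growth deficiency is one component of it. Section 9.3 has each variable reported separately.

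Birth weight, sex and gestational age are collected at the Pregnancy Outcome Follow-up (section 9.3.2.4), and weight at all six pediatric contacts (section 9.3.2.5).

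**The concern.** The label speaks of growth after birth, but the rule looks at size at one age. Size at a visit is the sum of size at birth and growth since then, and the rule does not separate them. Errors follow in both directions:

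- A small-born infant growing steadily along its own centile can be recorded as growth-deficient.
- An infant that loses much ground but stays at or above the 10th centile is not recorded.

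This matters more here than in a controlled study. Section 9.9 says that SMA itself may change outcomes and that no adequate unexposed SMA group can be assembled. If the infants are small at birth for any reason, that one fact can show up in two outcomes, fetal and postnatal, and a reader may take them as two separate signals. The issue arises in term infants at a single visit, so it does not depend on how prematurity or repeated assessments are handled.

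**Working it through.** The protocol gives no expected rate of growth deficiency, so there is no planned figure to reproduce. The check takes the two definitions together and asks what they imply.

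**Inputs from the protocol.** Cut-off for both outcomes: 10th percentile, z = −1.2816. Denominator for both: live births. Expected enrollment: 20 pregnancies (section 9.5).

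**Assumptions, not in the protocol.** Birth-weight z and visit-weight z are bivariate normal with correlation r. The range is 0.3 to 0.85: high at 1 month, lower by 24 months. Both percentiles are taken on compatible references.

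**1. Overlap with SGA at one visit.** Let B = P(both z below −1.2816). Then P(flagged | SGA) = B / 0.10 and P(flagged | not SGA) = (0.10 − B) / 0.90.

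| r | B | SGA flagged | Not SGA flagged |
|---|---|---|---|
| 0.3 | 0.0216 | 22% | 8.7% |
| 0.5 | 0.0324 | 32% | 7.5% |
| 0.6 | 0.0390 | 39% | 6.8% |
| 0.7 | 0.0468 | 47% | 5.9% |
| 0.85 | 0.0620 | 62% | 4.2% |

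At 10% SGA the overall rate is 10% by construction, and SGA-born infants make up 22 to 62% of those flagged.

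**2. Rate with no postnatal effect if SGA is more frequent.** Let p be the SGA share (assumed), with the conditional probabilities above held fixed. Rate = p × P(flagged | SGA) + (1 − p) × P(flagged | not SGA).

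- p = 20%, r = 0.3: 0.2 × 0.216 + 0.8 × 0.087 = 0.113.
- p = 20%, r = 0.85: 0.2 × 0.620 + 0.8 × 0.042 = 0.158.
- p = 30%, r = 0.3: 0.3 × 0.216 + 0.7 × 0.087 = 0.126.
- p = 30%, r = 0.85: 0.3 × 0.620 + 0.7 × 0.042 = 0.215.

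The range is about 11 to 22%, against 10%.

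**3. Falls that are not flagged.** From the 75th centile (z = 0.674) to the 12th (z = −1.175) is 0.674 + 1.175 = 1.85 SD, and the infant is not a case. To be flagged from the 75th centile it must fall 0.674 + 1.282 = 1.96 SD. If faltering is taken, for illustration, as a fall of at least 1.34 z since birth, 65 to 70% of such infants stay at or above the 10th centile at a single visit (simulation, r = 0.3 to 0.9).

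**4. Regression to the mean in a change score.** The mean birth z among SGA infants is −1.755. With no postnatal effect the expected change is (1 − r) × 1.755 upward: 1.23 at r = 0.3, 0.70 at r = 0.6 and 0.26 at r = 0.85. An infant at the 75th centile is expected to fall (1 − r) × 0.674: 0.47, 0.27 and 0.10. A raw change is therefore not neutral and has to be read given birth z.

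**5. Scale in this study.** If all 20 pregnancies gave one live birth each, 10% is 2 infants, and the exact 95% interval for 2/20 is about 1 to 32%. A rate of 11 to 22% would be about 2 to 4 infants.

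**The case against.** Several points on the other side stand.

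- **Overlap is not double counting.** A reader might infer that small infants are counted twice in one estimate. They are not: the outcomes are reported separately, and no estimate adds them.
- **Not every SGA infant is a case.** Under the assumed correlations, 38 to 78% of SGA infants are not flagged at a given visit, and some that are flagged will have lost further ground since birth. The two cut-offs need not coincide either, because SGA may use a country-specific chart.
- **The size is assumed.** Neither the correlations nor an SGA rate of 20 to 30% comes from the protocol, and the protocol does not say that maternal SMA causes small babies. The overlap is largest at early visits.
- **Precision is poor anyway.** The shift is small against an interval of about 1 to 32%, the analysis is descriptive, and external comparisons are optional.
- **A change score has its own faults**, as step 4 shows.

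It can also be said that a breakdown by SGA status belongs in the statistical analysis plan, and nothing in the protocol prevents one. But the definition itself is fixed in the protocol. Attained weight below the 10th percentile has the merit of being explicit, with a known reference rate of 10%; that is a reason to keep it, not to treat it as a measure of faltering on its own.

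**Conclusion.** The concern holds in a limited form. As written, the growth-deficiency component overlaps with SGA and does not by itself separate smallness at birth from impaired growth afterwards. That follows from the definitions, and for any positive correlation between birth and later weight SGA infants are flagged more often than others.

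The size is conditional. With r = 0.3 to 0.85, about 22 to 62% of SGA infants and 9 to 4% of others are flagged at one visit. With SGA also assumed at 20 to 30%, the rate absent any postnatal effect is about 11 to 22% instead of 10%. These figures describe the growth component at one visit, not the whole abnormal growth and development rate, which also includes development.

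The stronger reading, that the outcome cannot show impaired growth at all, is not supported. Infants who fall below the 10th centile are caught, other growth percentiles are estimated, and serial weights are available. This is a worthwhile and cheap improvement, not a flaw that invalidates the analysis.

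**What to change.** Keep the attained-weight measure. In sections 9.3.1.12 and 9.7.3.1.4:

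1. Report weight below the 10th percentile at each visit separately for infants born SGA and not born SGA.
2. Add, as a supplementary descriptive measure, each infant's change in weight z-score since birth. State one birth reference for this calculation in all countries, since section 9.3.1.3 allows different charts. Show the change beside the birth z-score so that regression to the mean can be allowed for.
3. State that attained weight below the 10th centile in an SGA-born infant is not on its own to be interpreted as postnatal faltering.

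The cost is some wording, extra table columns and a short listing; the weights, sex and gestational age are already collected. The downside is very small cells: about 2 SGA infants if 10% of 20 births are SGA (0.10 × 20). These displays should be labelled descriptive only.
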